**(2) Serious adverse events Adverse Event, SAE)**

It refers to adverse medical events such as death, life-threatening, permanent or severe disability or loss of function, the need for hospitalization or prolonged hospitalization, congenital abnormalities or birth defects, etc. that occur after the subject receives the investigational drug.

**(3) Important adverse events**

Refers to any clinical adverse event or significant abnormality in laboratory tests other than SAE that leads to targeted medical measures (such as discontinuation of drug, dose reduction and/or symptomatic treatment).

**(4) Adverse drug reactions drug reaction, ADR )**

In drug clinical trials, harmful or unexpected reactions to the human body caused by the test drugs are called adverse reactions.

**(5) Suspected and unexpected serious adverse reactions**

Refers to suspected and unexpected serious adverse reactions whose nature and severity of clinical manifestations are beyond the existing information in the investigator's brochure of the investigational drug, the instructions for use of the marketed drug, or the summary of product characteristics.

## 7.2 Recording of adverse events

The name, severity, time of occurrence, duration, treatment measures, and process of treatment of adverse events, important adverse events, and adverse reactions that occur from the beginning of the treatment period to the last visit should be recorded in the research medical record, and their relevance to the trial drug should be evaluated based on comprehensive consideration of comorbidities and concomitant medications, and recorded in detail by the researcher.

When adverse events or adverse reactions are found, researchers can determine whether to discontinue observation based on the patient's condition. Cases in which medication is discontinued due to adverse events or adverse reactions should be followed up and the results recorded in detail.

If any abnormality is found in the safety test indicators such as vital signs, physical examination, complete blood count, urine routine, liver function, kidney function, electrolytes, etc. during or after treatment, the test must be repeated at an appropriate time and comprehensively analyzed with the subjects' onset and treatment to determine whether it is related to the test drug.

### 7.3 Adverse event severity grading

According to the Common Adverse Events Evaluation Criteria (Common Terminology Criteria for Adverse Events 5.0, CTCAE) evaluates the severity of adverse events that occur during the trial, and the severity of adverse events is divided into 5 levels:

Grade 1: Mild; asymptomatic or mild; clinical or diagnostic observations only; no treatment required.

Grade 2: Moderate; minor, local or non-invasive treatment required; limitation of instrumental activities of daily living commensurate with age (instrumental activities of daily living include cooking, shopping for clothes, using the telephone, managing finances, etc.).

Grade 3: severe or medically significant but not immediately life-threatening; leading to hospitalization or prolonged hospitalization; causing disability; limiting self-care activities of daily living (self-care activities of daily living include bathing, dressing and undressing, eating, washing, taking medicine, etc., and not being bedridden).

Grade 4: Life-threatening, requiring urgent medical attention.

Grade 5: Death related to AE.

Records: Adverse events must be recorded in the original documents and the eCRF adverse event page, and the investigator shall determine the relevance of the adverse event to the trial drug and sign.

### 7.4 Determination of causal relationship between adverse events and drugs

Technical Guidelines for the Evaluation of the Correlation of Adverse Events in Clinical Trials of Drugs (Trial Implementation)  issued by the CDE , a comprehensive evaluation of the correlation between individual adverse events in clinical trials and the test drugs was conducted based on five evaluation points (whether there is a reasonable time relationship, whether it is consistent with the known drug mechanism, characteristics or known adverse reactions of the drug, destimulation results, restimulation results, and whether other reasonable reasons can be used to explain it). According to different situations, the judgment results are divided into five categories: related, very likely related, possibly related, possibly unrelated, and unrelated. Among them, "related, very likely related, and possibly related" are judged as adverse reactions and included in the calculation of adverse reaction incidence. See Table 1 and Table 2 for details.

**Table 1 Classification and basis for the results of adverse event correlation determination in drug clinical trials**

Five-point method	Judgment basis	dichotomy
related	

• Have a reasonable time relationship

• Comply with known drug mechanisms of action, properties, or known adverse reactions

• To stimulate positive

• Re-stimulation positive

• No other reasonable explanation

	
Probably related	

• Have a reasonable time relationship

• Comply with known drug mechanisms of action, properties, or known adverse reactions

• To stimulate positive

• Lack of positive evidence for rechallenge

• No other reasonable explanation

	Related
May be related	

• There is a reasonable time relationship ;

• lack of positive evidence of rechallenge ;

• Symptoms include any of the following:

① It is consistent with the known drug mechanism, characteristics or known adverse reactions , and the positive result is not stimulated, but it can also be explained by other reasonable reasons;

② The condition complies with known drug mechanisms, characteristics or known adverse reactions, lacks positive evidence of de-stimulation, and has no other reasonable explanation ;

③ It does not conform to the known drug mechanism of action, characteristics or known adverse reactions , and there is no other reasonable reason to explain the positive result.

④ It does not conform to the known mechanism of action, characteristics or known adverse reactions, lacks positive evidence of de-stimulation, and has no other reasonable explanation;

	

Probably not relevant	
 
Time relations cannot be ruled out
 
Lack of positive evidence for dechallenge
 
Lack of positive evidence for rechallenge
 
Symptoms include any of the following:           
 
① Although it is consistent with the known mechanism of action, characteristics or known adverse reactions, it can be explained by other more reasonable reasons;
 
② It does not conform to the known mechanism of action, characteristics or known adverse reactions, and can be explained by other reasonable reasons;
 
 
 
	Not relevant
Unrelated	
 
No reasonable time relationship
 
Does not conform to known drug mechanisms of action, properties, or known adverse reactions
 
Lack of positive evidence for dechallenge
 
Lack of positive evidence for rechallenge
 
Other reasonable reasons can be used to explain
 
	

Special Notes:

1. The correlation between adverse events and drugs shall be evaluated by relevant personnel with medical expertise.
2. Table 5 may not cover all situations in actual work. If it cannot completely correspond to the judgment basis in Table 6, you can refer to the professional judgment logic of the correlation between adverse events and drugs in the table to make the most reasonable judgment result.
3. When more information and evidence on the correlation between adverse events and drugs is collected during the progress of clinical trials, the previous correlation judgment results can be modified as needed, but sufficient reasons should be provided.
4. Lack of positive evidence for de-challenge includes the following situations: the de-challenge result is negative; de-challenge has not yet been performed; de-challenge is not applicable; Lack of positive evidence for re-challenge includes the following situations: the re-challenge result is negative; re-challenge has not yet been performed; re-challenge is not applicable.
5. In order to facilitate the work, the main contents of Table 1 can be simplified to Table 2. The special instructions for using Table 2 are the same as those for Table 1.

**Table 2 Adverse events and drug causal relationship judgment table**

Judgment result Judgment basis	Definitely related	Probably related	May be related		Probably not relevant	Unrelated
Is there a reasonable time relationship?	+	+	+		±	-
Does it conform to known mechanisms of action, properties	+	+	+	-	+	-

or known adverse reactions?								
To stimulate the results	+	+	+	- /?	+	- /?	- /?	- /?
Re-stimulation results	+	- /?		- /?			- /?	- /?
Are there other reasonable reasons to explain this?	-	-	+	-	-	-	+	+

**Note:**

- + indicates affirmative, or positive result;
- Indicates a negative result, or a situation where no result has been obtained yet;
- ± indicates that a temporal relationship cannot be ruled out;
- ++ means that there are other "more" reasonable reasons to explain it;
- /? indicates that the dechallenge/rechallenge result is negative, or dechallenge/rechallenge has not been performed, or dechallenge/rechallenge is not applicable.

## 7.5 Management of adverse events

If adverse events occur to the subjects during the trial, they shall be handled according to the following procedures:

After discovering that a subject has an adverse event, the researcher needs to inquire in detail about the subject's symptoms and signs at the time. If necessary, symptomatic treatment can be given first. The research physician will preliminarily assess the severity of the adverse event and its relevance to the trial drug, and provide further treatment advice:

- ① General adverse events: The outcome of the event can be closely and continuously observed or corresponding symptomatic treatment can be performed;
- ② Important adverse events: The research physician should inform the principal investigator promptly and take measures such as suspending treatment, adjusting drug dosage and providing targeted treatment according to the subject's condition. If necessary, the principal investigator may decide whether to urgently unblind the subject (if applicable).
- ③ Serious adverse events: Handle and report as the following "serious adverse events".
- ④ The research physician will treat the subject according to the condition of the patient. If the subject's injury exceeds the treatment capabilities of the research department, the relevant departments will be consulted and assist in handling the situation.

## 7.6 Management and reporting of serious adverse events

### 7.6.1 Handling of serious adverse events

- (1) When an SAE is considered, the attending physician shall notify the principal investigator or other responsible physician to be present. If the condition is serious, the project leader should be notified while emergency treatment is being given. If necessary, the trial drug should be discontinued immediately.

(2) If it is judged to be an SAE, appropriate treatment or rescue measures will be taken immediately according to the clinical manifestations and the standards of clinical rescue treatment of each specialty. If it is severe toxicity caused by drug overdose, the researchers will decide to give rescue measures such as accelerating drug excretion, maintain the stability of the patient's vital signs as much as possible, and perform ECG monitoring when necessary. If necessary, the relevant departments can be consulted and assist in handling the matter.

(3) When an out-of-hospital subject is diagnosed with an SAE and is unable to come for treatment, it is recommended that the subject return to the hospital or go to a local hospital for treatment in a timely manner, and immediately inform the project leader to obtain further treatment advice; if receiving treatment at a local hospital, contact the attending doctor to understand the specific situation and provide treatment advice. If necessary, bring the unblinding envelope and go to the local hospital for treatment or return to this hospital for treatment.

#### 7.6.2 Reporting of Serious Adverse Events

The reporting of SAEs should follow the SAE reporting procedures of the Chinese regulatory authorities or independent ethics committees. After an SAE occurs, the researcher must immediately report all SAEs in writing to the sponsor via email, and then provide a detailed, written follow-up report in a timely manner. For reports involving death events, the researcher should provide the sponsor and the ethics committee with the information they need, such as autopsy reports and final medical reports.

Sponsors should report SAEs to the relevant regulatory authorities in accordance with the requirements of regulatory authorities and local regulations, and during the implementation of the study, they will strictly abide by the "Standards and Procedures for Rapid Reporting of Safety Data during Drug Clinical Trials" to rapidly report suspected unexpected serious adverse reactions (SUSAR) to regulatory authorities. After receiving safety-related information from any source, the sponsor should immediately analyze and evaluate it, including the severity, relevance to the trial drug, and whether it is an expected event. Sponsors should rapidly report SUSAR to all researchers, clinical trial institutions, and ethics committees participating in clinical trials; sponsors should report SUSAR to drug supervision and administration departments and health and health authorities. After receiving the relevant safety information of the clinical trial provided by the sponsor, the researcher should sign for and read it in a timely manner, consider the treatment of the subjects, whether to make corresponding adjustments, communicate with the subjects as soon as possible when necessary, and report the SUSAR provided by the sponsor to the ethics committee.

The sponsor determines whether to report the event to the regulatory agency on an expedited basis based on the expected nature of the SAE and the results of the assessment of the relevance of the SAE to the investigational drug. The sponsor unblinds the case before the expedited report. SAEs for which the investigator has not assessed the causal relationship will be considered to be related to the investigational product. Therefore, the investigator should always record the most likely cause of the SAE in his or her judgment to avoid unnecessary unblinding of the case. After a more precise cause is

determined, the causal relationship of the investigational drug in subsequent follow-up reports of the trial can be revised.

During the implementation of the study, the "Standards and Procedures for Rapid Reporting of Safety Data during Drug Clinical Trials" will be strictly followed and the requirements of China's GCP and relevant regulations will be obeyed.

#### 7.7 Adverse events that were not relieved during follow-up

Adverse events that have not yet resolved at the study endpoint or have not been resolved must be followed up until one of the following events occurs:

- (1) Incident mitigation;
- (2) The event is stable;
- (3) if the baseline value is acceptable, the event returns to the baseline level;
- (4) When it is impossible to obtain additional information (the subject or the person who takes care of him/her refuses to provide additional information, and the subject is lost to follow-up despite follow-up efforts (at least 3 telephone contacts)).

Follow-up methods can be hospitalization, outpatient clinic, home visit, telephone, correspondence, etc.

### 8 Data Management

#### 8.1 Data Management Plan

This study uses an electronic data collection system (EDC) for data management. The data management plan is written by the project data manager based on the clinical trial protocol and registration observation form, describing the data management process, personnel division of labor, timetable and file archiving, etc., to ensure the consistency, effectiveness and standardization of data management work, promote communication and exchanges between various clinical research departments, and establish a high-quality database for statistical analysis. During the clinical trial, if the user needs to modify the data management plan, the data manager should be notified to revise and update it in real time, publish it to all relevant responsible personnel, and sign and confirm it.

#### 8.2 Database Management

The design and testing of the database shall be completed by the data management personnel based on the finalized clinical trial plan and the registration observation form. The data management personnel shall also mark the registration observation form and formulate variable descriptions. Logical verification settings shall be performed for fields with logical relationships according to the data verification plan.

After the database is established, it should be tested and verified, fully tested by relevant personnel, and entered after review and confirmation by the head of the data management department.

### 8.3 Data collection and recording

The registration observation form was designed according to the research protocol, and data collection was completed by clinicians.

The registration observation form is used as the original record and is imported into the EDC system, the database of this project.

### 8.4 Data Monitoring

The data verification plan is formulated by the data management department, medical technology department and project manager after fully understanding the design of the plan and discussing all the verification points of the plan's data management content. If modifications are required during the implementation process, the data manager will revise and update the version, and the above departments will sign and confirm again.

### 8.5 Data cleaning

Questions during the data verification process were generated in two forms: questions automatically generated by the online system and questions raised manually. The researchers or their authorized CRCs answered the questions online until the data were cleaned.

### 8.6 Data review

Before the data review meeting, samples will be drawn for quality control according to the ratio specified in the relevant SOP of the Data Management Department for the queries manually closed by the data administrator. If the quality control error rate is within the specified range, then the quality control is passed; if the quality control error rate is not within the specified range, samples will be drawn again for quality control according to the specified ratio. If it still fails, 100% quality control will be performed on all manually closed queries.

After the data cleaning is completed, the sponsor will be notified to hold a data review meeting. The sponsor, principal investigator, data management personnel, and statistician will conduct a final review of unresolved data issues and discuss the data set division according to the data review report.

After all the data are confirmed, the principal researcher will electronically sign the electronic data.

## 8.7 Locking and unlocking the database

### 8.7.1 Database Lock

Data locking should meet the following prerequisites:

- (1) All data have been collected and data processing such as data entry has been completed.
- (2) All data queries have been answered and the database has been modified based on the data queries.
- (3) If coding is required, ensure that the review of the medical data coding list has been completed to ensure the integrity and consistency of medical coding.
- (4) The final data logic and consistency check has been completed.
- (5) The data quality review has been completed and meets the requirements for statistical analysis.
- (6) All trial related documentation was updated and saved.

After the data manager confirms that the trial meets the above conditions, he/she will submit a written lock application, which will be signed and dated by trial-related personnel (data manager, biostatistician, project manager, sponsor, principal investigator). Once the written approval document for database locking is obtained, the database will be locked.

### 8.7.2 Database Unlock

In principle, locked data will not be changed unless there is very clear evidence that there are errors in the data and that they significantly affect the analysis results. Unlocking should provide written modification instructions from researchers and sponsors, detailing the content and reasons for the modifications. The version before unlocking is retained. Written signatures of senior management (such as the head of clinical implementation, the head of biostatistics, and the head of data management) are required. All revised data have audit traces. The database is locked again following the same process as the first time the database was locked.

## 9 Quality Control of the Study

Clinical research quality control runs through the entire process from protocol design, project implementation, data management, statistical analysis to report writing. Possible quality problems in the research are controlled in advance. The possible quality problems in this study involve multiple links of the project. The main quality control plan is as follows:

## 9.1 Bias Control

### 9.1.1 Selectivity bias control

Mainly in the design and implementation stage. The target population of the program design is accurate, and the hospital and doctor selection ensure the representativeness of the sample cases; once the doctor starts to register, there is no selection of registered cases, etc.

### 9.1.2 Information Bias Control

Information bias refers to the systematic errors caused by human factors in the integrity, authenticity, logic and measurement of patient data when collecting patient data. This study mainly controlled the possible information bias through the following methods.

- (1) Establish detailed data collection methods and strict quality control methods.
- (2) Collect information in a timely manner and ensure its accuracy.
- (3) Collect data strictly in accordance with the unified SOP to ensure consistency in data collection by all researchers.
- (4) By verifying the original data, the authenticity and integrity of the data can be guaranteed.
- (5) Regularly check missing values, abnormal values, logical relationships between indicators, etc. through electronic data logic verification and network verification, and send verification reports to the corresponding research centers for inspection, confirmation and modification.

### 9.1.3 Control of attrition bias

Loss-to-follow-up bias is inevitable in prospective studies. We should try to minimize the impact of patient loss-to-follow-up on the research results. We should strengthen physician education and increase physicians' attention to research. We should strengthen the responsibilities of research assistants and establish corresponding systems to minimize the number of lost-to-follow-up.

### 9.1.4 Control of confounding bias

The final data were controlled using statistical methods such as stratified analysis, standardization, multivariate analysis, and propensity score.

## 9.2 Program design and sample representativeness assurance

To ensure that the cases can represent the patients using Jingfang Heji, a multi-stage sampling method was used to select an estimated 10 hospitals from different regions and levels as case collection hospitals according to the regional distribution of clinical sales of Jingfang Heji and the hospital grade

distribution, as well as the sales share of hospitals of different grades. Based on the previous cases of using Jingfang Heji, a quota was used to allocate the sample size.

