## Program text

### 1 Background

Chikungunya fever is an acute infectious disease caused by chikungunya virus (CHIKV), transmitted by Aedes mosquitoes, and characterized by fever, rash, and joint pain. The first outbreak of chikungunya fever was confirmed in Tanzania in 1952, and the virus was isolated in 1956. The disease is mainly prevalent in Africa and Southeast Asia. Since 2004, outbreaks of chikungunya virus have become more frequent and widespread, partly because the virus has adapted to make it easier to spread through Aedes albopictus, and people of all ages are susceptible. In areas where Aedes mosquitoes exist, when Aedes mosquitoes reach a certain density and natural conditions are suitable, if CHIKV is introduced, it may cause an epidemic or outbreak.

On July 8, 2025, an imported case of Chikungunya fever occurred in Foshan, Guangdong. Till July 19th, there have been a total of 1,873 confirmed cases had been reported in Foshan. The rapid spread of the epidemic has brought certain treatment pressures to medical institutions. At present, there are no available vaccines or specific drugs in China, and the clinical treatment plan is mainly symptomatic treatment. In order to effectively respond to the recent surge in Chikungunya fever patients in medical institutions, the Chinese medicine expert team of Guangdong has discussed and formed a Chinese medicine agreement formula plan and applied it in clinical practice. In order to evaluate the effectiveness of this plan, this observational study is planned to be carried out.

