### 2 Purpose

- (1) To explore the epidemiological characteristics and Chinese medicine syndrome distribution of Chikungunya fever;
- (2) To evaluate the effectiveness and safety of Chinese medicine in the treatment of chikungunya fever.

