##### 4.2 Inclusion Criteria

- (1) Meets the suspected or confirmed diagnostic criteria for chikungunya fever;
- (2) Symptom onset  $\leq$  3 days before enrollment;
- (3) Actual prescribed treatment aligns with the study's group assignment (Chinese medicine, Western medicine, or combined therapy);
- (4) Sign the informed consent form.

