### 5 Observation Cohorts and Treatments

#### 5.1 Treatment Allocation by Cohort

- Chinese Medicine Group: Chinese treatments, which may include herbal formulas (e.g., decoctions, granules) or acupuncture, tailored to their syndrome differentiation (e.g., heat-clearing, detoxifying, or dampness-resolving therapies).;

- Western medicine group: Patients receive only standard Western medical care, which may include antipyretics (e.g., acetaminophen), NSAIDs for pain, and supportive treatments (e.g., hydration);
- Integrated therapy group : receive both Chinese and Western treatments.

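### Section 9.2 frames the sample around users of Jingfang Heji instead of chikungunya patients, and sections 3.1, 4.4 and 9.2 give enrolment rules that differ

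*Protocol*

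**What the plan says.** **Site frame.** Section 9.2 opens with its aim and method: "To ensure that the cases can represent the patients using Jingfang Heji, a multi-stage sampling method was used to select an estimated 10 hospitals". The hospitals come from different regions and levels, chosen "according to the regional distribution of clinical sales of Jingfang Heji and the hospital grade" distribution, and by the share of sales at each hospital grade. It ends: "Based on the previous cases of using Jingfang Heji, a quota was used to allocate the sample size".

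**Population and purpose.** The first inclusion criterion in section 4.2 is that the patient "Meets the suspected or confirmed diagnostic criteria for chikungunya fever". Section 5.1 defines three cohorts. The Chinese medicine cohort receives herbal formulas or acupuncture fitted to the syndrome. Another is defined as "Western medicine group: Patients receive only standard Western medical care". The third receives both kinds of treatment. The first objective in section 2 is "To explore the epidemiological characteristics and Chinese medicine syndrome distribution of Chikungunya fever". Section 1 says that an expert team "formed a Chinese medicine agreement formula plan and applied it in clinical practice", and that the study is meant to evaluate that plan. It does not name the plan's formula.

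**Enrolment.** The summary and section 3.1 set no number and take all patients who can be collected in the observation period. Section 4.4 takes all eligible patients at each centre, sorts them by actual prescription, and continues each group up to a target. Neither that target nor the quota in 9.2 is given a value.

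**The concern.** Section 9.1.1 rests its control of selection bias partly on the choice of hospitals and doctors, which is said to make the cases representative. Section 9.2 is the only text that describes how hospitals are chosen, and it describes a frame for users of one product. If it is followed as written, the sites reflect where that product sells, which need not be where chikungunya patients are treated. The syndrome and epidemiological distributions sought under the first objective would then carry a claim of representativeness that the design does not support.

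The enrolment rules matter for the comparison between groups. If each group closes when its own target is met, the groups may be recruited over periods that overlap only partly. The outbreak was moving fast. Section 1 dates an imported case to 8 July 2025 and adds: "Till July 19th, there have been a total of 1,873 confirmed cases had been reported in Foshan". If case mix or care changed over those weeks, treatment group and calendar time would be entangled.

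**Working it through.** The protocol states no total sample size, per-group target, quota or power calculation, so there is no figure to reproduce. The check is a comparison of the texts.

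**Step 1: does the frame in 9.2 match the study population?**

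| Item | Section 9.2 | Rest of the protocol |
|---|---|---|
| Who is to be represented | Users of Jingfang Heji | Suspected or confirmed chikungunya patients (4.2) |
| Basis for choosing sites | Product sales and hospital grade | No other basis stated |
| Basis for allocating the sample | Past use of the product | Actual prescription, all eligible patients (4.4) |
| Treatment concerned | One named product | Chinese, Western or combined care (5.1) |

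The product does not appear in the title, summary, background, objectives, eligibility criteria or cohort definitions. Suppose that it were the expert team's formula, which the protocol does not say. The frame would still not describe the Western-only cohort, or patients given acupuncture or other formulas. The mismatch therefore does not depend on what the product is.

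**Step 2: do the enrolment rules agree?**

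- Summary and 3.1: everyone who can be collected, with no ceiling.
- 4.4: all eligible patients, each group running to a target that is not stated.
- 9.2: a quota that is not stated, set from past product use.

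Before any target or quota is reached, the three rules admit the same patients at a given site. After that they part. The first rule still admits the next eligible patient on that treatment or at that hospital, and the other two need not. Without the numbers, nobody can say when this happens. Two centres could act differently and each cite the protocol.

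**Step 3: can the analysis absorb the difference?** Section 9.1.4 plans stratification, standardisation, multivariable analysis and propensity scores. Where two groups are recruited in the same weeks, enrolment date could be handled by such methods. Where one group has closed and another is still open, there are no concurrent patients to compare, and none of these methods supplies them.

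**Step 4: what can be put in numbers?** Only the speed of the outbreak. From 8 to 19 July inclusive is 12 days, and 1,873 / 12 is about 156 confirmed cases a day. These are reports for the whole of Foshan, not study accrual. The figure shows that calendar time could matter, not that it biased anything.

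**The case against.** The best reply is that 9.2 does little harm in practice. Section 4.4 takes every eligible patient at each centre, so Western-only patients can be enrolled at hospitals chosen by product sales. A hospital without chikungunya patients contributes nobody. The protocol does not show that sales and cases diverge, nor that 9.2 was ever applied. All of this stands, and it limits the point to the stated frame and to the claim built on it. It does not make the frame right, because 9.1.1 relies on hospital selection for representativeness.

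Several stronger readings are tempting but not supported:

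- *That 9.1.1 requires every patient to be enrolled.* It only bars the doctor from picking among cases once registration has begun. A target does not breach it.
- *That 4.4 contradicts itself.* It can be read as taking every eligible patient until the target is met. The conflict is with the summary and 3.1, which set no target.
- *That the quota in 9.2 closes treatment groups.* It stands in a text on choosing hospitals and may well be a quota per hospital. It still conflicts with 3.1, but the risk of groups closing at different times rests on 4.4 alone.
- *That the length of follow-up is unclear.* Sections 4.5 and 5.2 make the 28 days a per-patient period. What is left is loose wording in 3.1, which uses the same term for recruitment.
- *That the loss of overlap between groups can be quantified.* Any percentage would need an assumed prescribing mix and assumed targets, and would reflect those assumptions only.

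**Conclusion.** The point holds in two parts. First, the only stated site-selection frame is for a population other than the one studied. It cannot support the representativeness claim or the first objective. This follows from the text alone, and confidence is high. Second, the summary and 3.1, 4.4, and 9.2 do not give one enrolment rule, and the cohorts they produce differ once a target or quota fills.

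The size of either effect is unknown. A reader might infer that the syndrome distribution or the group comparison is biased, but the protocol has no data on sales against cases, or on case mix over time, that would show it. Partial overlap of recruitment periods is a risk only if groups are closed separately under 4.4, which gives no closing procedure. The protocol should be corrected on both parts. Neither part rests on the absence of a power calculation.

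**What to change.** - **Section 9.2:** replace the Jingfang Heji frame and quota with the rule by which sites for chikungunya patients are chosen. The section is in the past tense. If sites or quotas were already set by the product's sales or use, that cannot be undone by deleting the text: report it and limit the representativeness claim accordingly.
- **Sections 3.1, 4.4 and 9.2:** state one rule. Enrol all consecutive eligible patients in all three groups between stated calendar dates, with a common closing date, and delete the target clause in 4.4. This agrees with the summary and 3.1 and keeps the groups concurrent.
- **Section 3.1 (wording only):** state the recruitment window separately from the 28-day follow-up of each patient.

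The cost is rewording, with no patients beyond those the all-patient rule already takes. The downside is that group sizes follow prescribing practice: they will be unequal, and the rarest group may be small.
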